11.7 Viability testing

Randomly selected used opened packs of unused sachets from study preparation packs will be sent refrigerated to central laboratory for quality control check to confirm that the total number of live microorganisms is consistent with that stated in the certificate of analysis by the manufacturer, (450 billion lactic acid bacteria and *bifidobacteria*). However, given the existing quality control procedures for the manufacture of this product, identification of the individual bacterial strains contained in VSL[#]3 will not be undertaken. Similarly the placebo sachets will be tested to confirm the absence of active microorganisms.

12 Pharmacovigilance

12.1 Definitions

The following definitions are in accordance with both the Medicines for Human Use (Clinical Trials) Regulations 2004 (SI2004/1031) and the subsequent amendment regulations (SI2006/1938) and ICH-GCP:

Adverse Event (AE): Any untoward medical occurrence in a clinical trial participant to whom an IMP has been administered and which does not necessarily have a causal relationship with this treatment. An AE can therefore be any unfavourable and unintended sign (including abnormal laboratory finding), symptom, or disease.

Adverse Reaction (AR):

Any noxious and unintended response in a clinical trial participant to whom an IMP has been administered, which is related to any dose administered. A "response" to a medicinal product means that a causal relationship between a medicinal product and an adverse event is at least a reasonable possibility, i.e. the relationship cannot be ruled out.

Serious Adverse Event (SAE): Any adverse event that:

- Results in death,
- Is life-threatening,*
- Required hospitalisation or prolongation of existing hospitalisation,**
- Results in persistent or significant disability or incapacity,
- Consists of a congenital anomaly or birth defect,
- \bullet Other medically important condition, as assessed by the GP or the CI/delegated Safety Reviewer,***

* *Note*: The term "life-threatening" in the definition of serious refers to an event in which the participant was at risk of death at the time of the event; it does not refer to an event which hypothetically might have caused death if it were more severe.

** *Note*: Hospitalisation is defined as an inpatient admission, regardless of the length of stay, even if the hospitalisation is a precautionary measure, for continued observation. Pre-planned hospitalisation e.g. for preexisting conditions which have not worsened or elective procedures does not constitute an AE.

*** *Note*: other events that may not result in death are not life-threatening, or do not require hospitalisation may be considered as a SAE when, based upon appropriate medical judgement, the event may jeopardise the participant and may require medical or surgical intervention to prevent one of the outcomes listed above.

Serious Adverse Reactions (SARs): A SAR is defined as any "reaction" occurring in a clinical trial participant for which there is a reasonable possibility that it is related to the IMP at any dose administered.

Suspected Unexpected Serious Adverse Reactions (SUSAR): These are **SARs** which are classified as 'unexpected' i.e. an adverse reaction, the nature and severity of which is not consistent with the applicable product information for VSL[#]3 probiotic.

12.2 Reporting procedures

All serious adverse events should be reported following randomisation up until the end of the eight week follow-up period. Depending on the nature of the event, the reporting procedures outlined in this protocol should be followed. Any queries concerning serious adverse event reporting should be directed to the study coordination centre in the first instance. A flowchart (Figure 2) is given below to illustrate reporting procedures.

12.2.1 Non serious AR/AEs

Since the study intervention is defined as a probiotic, which is a nutritional supplement, containing known species of live bacteria that are included in foods and commercially available, we do not request all adverse events (AEs) be reported. All expected adverse reactions will be recorded using the symptoms (Illness severity and symptoms CRF) section in the Daily Diary.

12.2.2 SAEs

All SAEs and reactions must be reported immediately by the care home manager or a senior staff member to SEWTU. A completed SAE form for all events should be faxed to SEWTU within 24 hours of knowledge of the event (or the next working day) on [name]. A flowchart is provided in Figure 3 to aid in the reporting procedures.

Responsibility for the reporting of SUSARs and other SARs to the regulatory authorities (MHRA) and the REC are as follows:

- SUSARs which are fatal or life-threatening must be reported not later than 7 days after the sponsor is first aware of the reaction. Any additional relevant information must be reported within a further 8 days.
- SUSARs that are not fatal or life-threatening must be reported within 15 days of the sponsor first becoming aware of the reaction.

SAEs will be reported from the time a participant is randomised onto the study and for the 8 weeks follow up duration.

SAEs will be followed up by the PAAD team until they are resolved or the investigator assesses them as chronic or stable. The follow up and outcome of SAEs will be document in the appropriate CRF.

A list of all SARs (expected and unexpected) must be reported annually to the MHRA and REC.

12.2.3 SAEs

Due to the agreement between SEWTU and VSL/Actiel, all SAEs will be reported to the manufacturer of VSL[#]3.

Contact details for reporting SAEs For the attention of the PAAD TRIAL MANAGER Please Fax SAE forms to: [name] [contact] (Mon to Fri 09.00 - 17.00)

The SEWTU Standard Operating Procedure (SOP) for reporting any Serious Adverse Events (SAEs)) will be used to report to the sponsor, MHRA and Research Ethics Committee (REC).

12.3 Evaluation of SAEs

The principle investigator should ensure that all SAEs known to the care home staff are identified and each one assessed for causality and reported to SEWTU immediately as described in Figure 2. They will be evaluated by staff at SEWTU and one of the chief investigators (or their delegate) for seriousness, expectedness and causality. Investigator reports of SUSARs will be reviewed immediately and those that are SUSARs identified and reported to the regulator authority. In the event of a disagreement between the PI and CI regarding causality of an SAE, the highest relationship (i.e that closer to definitely related) will be reported. Expectedness of an SAE should be assessed in relation to the known adverse reactions described in the product characteristics for VSL[#]3 or the placebo provided by VSL/Actiel. Expected adverse reactions with the study interventions are listed below:

- excessive flatulence,
- bloating,
- skin rashes,

Please note: Although the information provided in the above table was comprehensive at the time the current protocol version was produced, the list of side effects may have been subsequently updated and the site staff /investigator should refer to an up to date SmPC.

12.4 Assessment of intensity

The intensity of all SAEs should be assessed by the PI according to the following definitions:

Mild – Does not interfere with SUs usual function
Moderate – Interferes to some extent with SUs usual function
Severe – Interferes significantly with SUs usual function

It should be noted that the severity and seriousness of an SAE are not the same classification, such that an SAE classified as severe (for example a headache) is not necessarily an SAE (unless it also meets the definition of an SAE in Section 7.2):

12.5 Causality

Causality of every SAE should be assessed using clinical judgement based on the information available to determine the relationship between the SAE and the intervention received by the participant. For the purpose of this trial, relationships will be classified as one of the following: not related; unlikely to be related; possible related; probably related; definitely related.

[contact]

13 Study procedures

13.1 Training of staff

Training materials will be designed from the training plan used during PAAD Stage 1 and feedback from Sub-Study 3 (see above), where the views of CHS were established about necessary staff training.

The training schedule for staff will be tailored to meet the needs required by each individual study site. The training package will be designed specifically to train different staff groups, depending on the roles and responsibilities of the staff, e.g. Health Care Workers (HCWs) will be trained specifically on tasks of stool sampling, handling, storage and posting, but overall responsibility of delivering this task will remain with the senior care home staff. Designated staff members will have the responsibility of cascading training and delegating specific protocol tasks to other study site staff. Depending on the individual circumstances of the care home, the most appropriate members (i.e.at least one senior member of staff) will receive ICH GCP training and certification prior to commencement of SU recruitment. This member of staff will also have received training in the assessment of mental capacity. Taking informed consent will be carried out by ICH GCP trained senior CHS and RNs, however all CHS with designated roles and responsibility on the PAAD Study will be encouraged to receive ICH GCP training.

For the handling of the study medication designated dispensing staff at the care home will be provided with training at the start of the study, while further training will be provided by the researchers on an on-going basis as required by CHS. Emphasis will be placed on the use of designated cold storage (including temperature monitoring) of the study medication and recording of their administration and reconciliation for each SU randomised. Training will be provided for the maintenance of the level of stock of the study medication at the care home, which will be monitored by the researchers to ensure adequate supply.

13.2 Training of GPs and Responsible Clinicians

A GP at each practice linked to participating care homes will be selected as a champion of the PAAD Study. These champions will be asked to liaise with other GPs in the practice, any responsible clinicians, and the out of hours service providing GMS for the practice during evenings, weekends and bank holidays. Each champion will receive training on the PAAD Study, including assessment of eligibility and authorisation of the probiotic/placebo in the event of an antibiotic being prescribed.

GPs will be reimbursed for their time spent on the PAAD Study.

13.3 Data collection/assessment

Table 1 details the PAAD Case Report Forms (CRFs) and questionnaires, time points for data collection and who has overall responsibility for collecting the data. Training for completion of trial CRFs will be provided to the applicable care home staff prior to the trial commencing. CRFs should be completed in black ball point pen, with unique service user ID number, Study Medication Number (where applicable) initials and date of birth recorded on the header of each individual form. Incorrectly entered information should only be amended on the original CRF prior to photocopying. Corrections should be made by deleting with a single line through the entry and writing the correct value alongside the box; all amendments should be initialled and dated. CRFs will be Non carbon copied where possible. The top copy should be sent to the PAAD TM or picked up by the SEWTU PAAD team/research nurse and the bottom copy kept in the SU PAAD file.

13.3.1 Allocation of study medication

The procedure for allocation of study medication is detailed in Section 9.6.1

13.3.2 Baseline assessments

Following the completion of the Eligibility for Study Medication CRF, baseline assessments will take place. Using the Medical Information CRF the SUs clinical frailty and nutritional status will be recorded, as well as a detailed list of medical history and concurrent medication. The EQ-5D Quality of Life questionnaire will also be completed at this time point.

13.4 Follow-up

Service Users prescribed with antibiotics will be followed up for eight weeks from the date that they are allocated study medication.

13.4.1 Daily Diary

A diary will be kept for an eight week follow-up period. The diary will record information on adherence to the study intervention over the 21 day period and for the antibiotic treatment period; study adverse events and symptoms related to diarrhoea severity and illness severity.

13.4.2 Stool Chart

For each week of the study follow-up period, a stool chart will record the frequency and type of stool (according to the BSC).

13.4.3 Quality of Life

Health-related quality of life will be assessed at the beginning of each week for the duration of the eight-week follow-up period via the EQ-5D.

13.4.4 Healthcare Resource Usage

A record of the healthcare resource usage will be collected for each service user at the end of the 8 week follow-up period. This enables an assessment of any use of NHS resources, (including GP and practice nurse consultations, procedures, investigations, hospital appointments, A&E attendances and any hospital inpatient admissions).

13.4.5 Medication use

A record of the medication used post randomisation for the 8 weeks of follow up will be collected.

13.4.6 Stool sampling

Diagnostic stool samples will be collected only at times when diarrhoea occurs during follow up and a second sample will be collected if diarrhoea continues for greater than 48 hours. Diarrhoea, for the purposes of this study, is defined as 3 or more loose stools at BSC type 5 – 7, in a 24 hour period, following a period of normal stool consistency. Sampling will be carried out by a CHS / study research nurse. The sample will be put into containers provided by the study team. This container must be labelled with the participants ID number, initials and date of birth and sent by 1^{st} Class Royal Mail using Post Office approved SafeboxesTM, a method that meets legal requirements. The sample must be sent within 48 hours of taking the sample, in order to be analysed within 72 hours. The sample will be sent to the Public Health Wales Microbiology laboratory for the determination of microbial content, speciation of *C. difficile* culture, toxins A and B and as well as screening for carriage of antibiotic resistant bacteria. Any cultured *C. diff* isolates will be ribo-typed, toxin tested, and have antimicrobial sensitivity testing done, as well as screening for carriage of antibiotic resistant bacteria. All isolates will be retained and stored at -70°C.

The research team will receive results of study diagnostic stool sample analyses from the Microbiology laboratory.

		Defere	At time of	At time of antibiotic			F	ollow Up (wee	o Period ks)			
	Data Type	Berore study recruitment begins	consent	prescribed/ eligibility checked and confirmed	1	2	3	4	5	6	7	8
1.	Care Home	X										
2.	Eligibility for enrolment		Х									
3.	Eligibility for Study Medication			X								
	a) Medical information			X								
4.	Follow up diary											
	a) Study medication and antibiotic adherence				D	D	D	D				
	 b) Illness severity and symptoms 				D	D	D	D	D	D	D	D
	c) Stool monitoring				D	D	D	D	D	D	D	D
	d) Additional Medication				W1	W1	W1	W1	W1	W1	W1	W1
	e) Quality of life				W2	W2	W2	W2	W2	W2	W2	W2
	f) Healthcare resource use											E
5.	Diagnostic Stool Sample				I<			as req	uired			>l
6.	Withdrawal		I<			as	required					>l
7.	SAE				I<			as req	uired			>l

Table 1 – CRF schedule

D = Questions are to be completed on a daily basis

W1 = Questions should be completed on weekly basis for that week

W2 = Questions should be completed at the start of the week based on that day

E = Questions are to be completed at the end of the 8 week follow-up

14 Statistical considerations

14.1 Randomisation

Randomisation will be carried out using random permuted blocks. Computer-generated random numbers will be produced to select a block of allocations from the set of all possible permutations of allocations (on a 1:1 ratio) given a particular block-size before the trial begins.

14.2 **Primary outcome measures**

The primary outcome is the occurrence of at least one episode of AAD during the eight weeks following randomisation. AAD is defined as three or more loose stools (defined as a 5 – 7 on the BSC) in a 24 hour period following a period of normal stool consistency.

14.3 Secondary outcome measures

- The occurrence of *C.difficile*-associated diarrhoea (CDAD). This is defined as having a diagnostic stool sample (following the occurrence of AAD) that is found to contain *Clostridium difficile* toxin A or B.
- Health-related quality of life measured using the EQ-5D.
- The duration, frequency and recurrence of AAD. The duration of AAD is defined as the total number of consecutive 24 hour periods that a SU has AAD (as per our definition in 14.2.).
- The frequency of AAD is the number of episodes of AAD a SU experiences during the eight week follow-up period. AAD episodes are only considered unique if they are separated by a period of at least three days of "normal" stool consistency
- Recovery from the illness that triggered the prescription of antibiotic treatment. A single item will be asked daily and will capture the illness severity of the SU on a particular day
- Adherence to the study intervention and antibiotic treatment. Adherence will be defined as full (all doses on a particular day), partial (at least one dose but not all) and not (no doses on a particular day).
- Healthcare Resource Use. Costs will incorporate information on GP and practice nurse consultations, other medication, procedures, investigations, hospital appointments, A&E attendances and any hospital inpatient admissions and will be measured at the end of the eight-week follow-up period.
- Unplanned (not a routine hospital appointment) hospitalisation, both all-cause and AAD-related.

- Adverse events. These include reported symptoms such as vomiting, abdominal pain, excessive flatulence, bloating, skin rashes.
- All-causes mortality during the eight week follow-up period.

14.4 Sample size

A total of 400 SUs (200 per arm) will need to be randomised in order to achieve 80% power, at the 5% level, to detect a 50% relative reduction in the incidence of antibiotic associated diarrhoea in those given probiotic intervention alongside antibiotic treatment, compared to placebo alongside antibiotic treatment. This sample size has been adjusted for a 20% loss to follow-up/withdrawal.

Taking into consideration the results from the interim analysis performed in PAAD Stage 1 and a more recent interim assessment of antibiotic prescribing and AAD (from first antibiotic prescription), assuming an AAD incidence of 25% in the placebo arm (lower confidence limit quoted in Appendix 3), in order to randomise 400 SUs we will need to obtain advanced consent from at least 607 SUs (assuming 66% will be prescribed at least one course antibiotics during the 12 month monitoring period and subsequently randomised) and will need to approach approximately 1214 SUs in order to achieve this consent rate (assuming only 50% will provide consent). With an average of 60 SUs per home, we will need to recruit from a minimum of 21 care homes. In order to allow for care home drop-out, larger than anticipated withdrawals/drop-out/declines and smaller than anticipated care homes, we aim to recruit from 24 care homes.

15 Analysis

15.1 Main analysis

For the primary analysis, a logistic regression model will be constructed with AAD during eight week follow-up (Yes/No) as the dependent variable and study arm (probiotic/placebo) as an explanatory variable. The analysis will be adjusted for:

- The potential clustering of SUs within care homes via multilevel analysis
- Potential, pre-specified confounding/risk factors as specified in the Statistical Analysis Plan

The primary analysis will be based on the intention to treat principle.

15.1.1 Secondary analyses

In a similar way to the primary analysis, a logistic regression model will be constructed, with 'Returned positive stool sample for *Clostridium difficile* toxin A and B following AAD' (YES/No) as the dependent variable and study arm (probiotic/placebo) as an explanatory variable, in order to investigate the effect of probiotics on the development of CDAD during the eight week follow-up period. In an analogous way to the primary, this analysis will adjust for clustering (if present) and confounding factors.

Generalised linear models will be used to order to:

- Investigate the effect of probiotics on the duration, frequency and recurrence of AAD during the eight week follow-up period
- Investigate the effect of probiotics on all-cause hospitalisations during the eight week follow-up period
- Investigate the effect of probiotics on illness recovery
- Investigate the effect of probiotics on antibiotic adherence
- Investigate the relationship between study intervention adherence and AAD/CDAD
- Investigate the relationship between antibiotic adherence and AAD/CDAD
- Investigate the effect of probiotics on mortality in the eight week follow-up period
- Investigate the effect of probiotics on both all-cause and AAD-related hospitalisation during the eight week follow-up period

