Trial participants	Adults who are usually resident in participating nursing or dual-registered care homes in the UK who are prescribed antibiotics during the study period.		
Planned sample size	400 SUs (200 per arm)		
Follow-up duration	SUs will be followed up for eight weeks from the date of randomisation.		
Planned trial period	24 months		
Primary objective	To compare the effectiveness of probiotics vs. placebo, taken in conjunction with antibiotics, on the incidence of AAD in care home SUs.		
Secondary objectives	• To compare the effectiveness of probiotics vs. placebo, taken in conjunction with antibiotics, on the duration and severity of AAD in care home SUs.		
	• To compare the effectiveness of the probiotics vs. placebo in reducing the incidence of C. difficile -associated diarrhoea (CDAD) in care home SUs.		
	• To evaluate the impact of probiotics on Quality of Life (QoL) in care home SUs.		
	• To evaluate the cost effectiveness of probiotics for AAD in care home SUs.		
Primary endpoint	Occurrence of at least one episode of AAD during the eight weeks following randomisation.		
Secondary endpoints	 Proportion of stool samples positive for Clostridium difficile toxin A or B from SUs who develop AAD during the eight week follow-up period. Duration, frequency and recurrence of AAD during the eight-week follow-up period. QoL, measured using EQ-5D at the time of randomisation and each week during the eight-week follow-up period. Recovery from illness that triggered antibiotic treatment. Healthcare Resource Use, including GP and practice nurse consultations, other medication, procedures, investigations, hospital appointments, A&E attendances and any hospital inpatient admissions, measured at the end of the eight-week follow-up period. Upplanned hospitalisations, including all-cause and AAD related, during 		

	 the eight-week follow-up period. Adverse Events: e.g. vomiting, abdominal pain, excessive flatulence, bloating, skin rashes, during the eight-week follow-up period. Adherence to the antibiotic, probiotic/placebo treatment course. All causes of mortality in the 8 week follow up period.
Investigational	• VSL# 3, freeze dried lactose free sachet containing 4.4g of a mixture of
medicinal products	450 billion live lactic acid bacteria and bifidobacteria. These bacteria
	consist of eight strains of potentially beneficial bacteria:
	• Streptococcus thermophilus,
	• Bifidobacterium breve,
	 Bifidobacterium longum,

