5.2 Secondary objectives

- To compare the effectiveness of probiotics vs. placebo, taken in conjunction with antibiotics, on the duration and severity of AAD in care home SUs.
- To compare the effectiveness of the probiotics vs. placebo in reducing the incidence of *C. difficile*-associated diarrhoea (CDAD) in care home SUs.
- To evaluate *th*e impact of the probiotics on Quality of Life (QoL) in care home SUs.
- To evaluate the cost effectiveness of probiotics for AAD in care home SUs.

6 Study design

This is a phase III individually randomised, double-blinded, parallel group trial of probiotic versus placebo for care home SUs who are prescribed antibiotics for acute infection. A total of 400 SUs from approximately 24 care homes in Wales (and potentially England) will be randomised.

The target population are SUs resident in care homes under a long-term care plan. Data entry, management and analysis will be conducted centrally at the South East Wales Trials Unit (SEWTU).

7 Centre and Investigator selection

Care homes located in Wales and if necessary from the South West and other parts of England will be approached to take part in the PAAD Study. We will seek agreement about participation in the study from the manager and the owner of suitable care homes. An agreement, detailing roles and responsibilities will be signed by the care home manager and the owner of the care home. The care home manager will be defined as the Principal Investigator (PI) at the care home, as the study site, and by Cardiff University as the sponsor of the study.

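### The CDAD endpoint is stated inconsistently: either toxin in the definition but both in the model, and a share of AAD stool samples in the synopsis that does not measure CDAD incidence

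*Protocol*

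**What the plan says.** The secondary objective in 5.2 of the protocol is "To compare the effectiveness of the probiotics vs. placebo in reducing the incidence of" CDAD in care home residents. The endpoint that serves it is described in three places.

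- **Synopsis, secondary endpoints:** "Proportion of stool samples positive for" *C. difficile* "toxin A or B from SUs who develop AAD during the eight week follow-up period". The unit is the sample, the denominator is samples from residents with AAD, and either toxin suffices.
- **Section 14.3:** the occurrence of CDAD, defined as a diagnostic sample ("following the occurrence of AAD) that is found to contain *Clostridium difficile* toxin A or B"). The unit is the resident, and either toxin suffices.
- **Section 15.1.1:** a logistic regression, built like the primary one, of a returned sample positive for *C. difficile* "toxin A and B following AAD' (YES/No) as the dependent variable". Its purpose is given as "in order to investigate the effect of probiotics on the development of CDAD during the eight week follow-up period". The unit reads as the resident, and taken literally both toxins are required.

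Section 13.4.6 adds that "a second sample will be collected if diarrhoea continues for greater than 48 hours", so one resident can supply several samples. Nothing in the protocol reconciles these statements.

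**The concern.** There are two separate discrepancies.

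The first is the toxin rule. A sample with toxin A only, or toxin B only, meets the definition in 14.3 but is a non-event in the 15.1.1 model as worded. Few CDAD events are expected, so the case definition should not depend on which section is followed.

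The second is the unit and denominator in the synopsis. A share of samples among residents who develop AAD conditions on an event after randomisation, and it is the very event the probiotic is meant to prevent. It also weights longer or repeated episodes more heavily through extra samples. It answers a different question (of the AAD that occurs, how much is *C. difficile*?) from the objective (how many residents get CDAD?). If it were reported as the endpoint, it could hide a benefit or suggest a harm that is not there.

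**Working it through.** The protocol states no CDAD event rate, sample size or power, so there is no figure of its own to reproduce. The check uses its planning rates.

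**Inputs**
- AAD on placebo 25%, relative reduction 50%, hence 12.5% on probiotic; 200 per arm (14.4).
- *C. difficile* share of AAD: 8/34 = 23.5% of Stage 1 samples (Appendix 2). Section 4.2 shows this is culture positivity, so its use for toxin positivity is an assumption. Section 4.1.3 gives 20–30% as a background range.
- One sample per AAD case, and the same share in both arms (assumptions).

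**Per-resident CDAD** = AAD rate × share
- Placebo: 0.25 × 8/34 = 0.0588, or 200 × 0.0588 = 11.8 cases.
- Probiotic: 0.125 × 8/34 = 0.0294, or 5.9 cases.
- Risk ratio: 0.0294 / 0.0588 = 0.50.

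**Synopsis proportion** = CDAD cases / AAD cases
- Placebo: 11.8 / 50 = 23.5%.
- Probiotic: 5.9 / 25 = 23.5%.
- Ratio: 1.00.

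The share cancels, so neither ratio depends on its value. At 20% the per-resident rates are 5.0% vs 2.5%; at 30% they are 7.5% vs 3.75%. The risk ratio stays 0.50 and the synopsis ratio 1.00.

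**If CDAD is halved but AAD falls by a fraction r**, the synopsis ratio is 0.50 / (1 − r):

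| AAD reduction r | Synopsis ratio |
|---|---|
| 0 | 0.50 |
| 25% | 0.67 |
| 50% | 1.00 |
| 60% | 1.25 |

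The per-resident risk ratio is 0.50 in every row. The synopsis measure therefore follows the per-resident effect only when AAD does not change, and it shows nothing exactly at the protocol's design effect.

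**Either toxin against both.** Let f be the fraction of A-or-B positives that carry both toxins. Expected placebo events under the 15.1.1 wording are 11.8 × f. The documents give no value for f. As an assumed range only, f = 0.5 gives 5.9 and f = 1 gives 11.8. If f is the same in both arms, the risk ratio stays at 0.50 and the loss is in events, not in direction.

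**The case against.** The strongest reply is that the synopsis proportion is not what the trial plans to analyse. Section 15.1.1 fits a Yes/No outcome in the manner of the primary analysis, to study the development of CDAD; that is per resident and matches both 14.3 and the objective. No section models a proportion of samples. A reader might infer from the arithmetic that the planned analysis would miss a halving of CDAD or abandon the randomised comparison. The protocol does not support that: the equal-proportions result belongs to the synopsis wording alone. Nor are there three mutually incompatible definitions. Sections 14.3 and 15.1.1 share the unit, and the synopsis and 14.3 share the toxin rule.

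On the toxins, the *and* in 15.1.1 may simply echo the laboratory's test list in 13.4.6. That is plausible, but as written it is a stricter case definition than 14.3, and one word settles it.

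A reader might also take the word *returned* in 15.1.1 to mean that AAD with no sample result is coded as no CDAD, and might support this with Stage 1, where 34 samples were analysed against 51 prescriptions with AAD. The documents do not support this either. The phrase can mean only a sample that tested positive, and handling of missing results is commonly left to the SAP. The 34 and 51 count different things (samples and prescriptions) at an interim cut while Stage 1 was still running, so their ratio is not a rate of missing samples.

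Finally, this is one secondary endpoint with little power under any wording. At about 12 vs 6 events, a two-sided 5% normal-approximation comparison with 200 per arm has roughly 30% power. That limits the severity; it does not remove the contradiction.

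**Conclusion.** The inconsistency is real and of moderate importance. The model in 15.1.1, read literally, does not use the case definition in 14.3 and the synopsis; the size of the resulting loss of events cannot be derived from the documents. Separately, the synopsis endpoint does not measure the stated objective. At the design effect it gives a ratio of 1.00 where per-resident CDAD has a risk ratio of 0.50 (about 5.9% vs 2.9%). The two ratios rest on AAD being halved, an equal *C. difficile* share of AAD in both arms and one sample per case. The absolute rates rest also on the culture-based 8/34. The primary outcome, its analysis and the sample size are not affected.

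**What to change.** Use one definition in the synopsis, 14.3 and 15.1.1. Per randomised resident: at least one diagnostic stool sample positive for toxin A or toxin B following AAD within eight weeks of randomisation (Yes/No). Count each resident once however many samples are sent, and include all randomised residents in the comparison, as in the primary analysis. In 15.1.1 this means replacing *and* with *or* in the toxin rule. In the synopsis it means replacing the proportion of samples with the per-resident outcome. The proportion of samples positive can still be reported by arm as description, without a treatment-effect interpretation.

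The cost is a wording amendment in three places. No new data, visits or laboratory tests are needed, since 13.4.6 already has both toxins determined.
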